#### 9.6 VITAL SIGNS

Blood Pressure (sitting position after 3 minutes rest) will be measured.

#### 9.7 MEDICATIONS

All medications must be reported on the appropriate case report form (CRF) through the end of study. Medications must remain stable from Screening/Baseline through the Therapy Phase of the study. The only exception is medications may be changed for subject health or safety reasons (but not specifically to attempt to reduce weight loss or appetite).

#### 9.8 QUESTIONNAIRES

All subjects will be required to complete the Patient Preference Survey and PHQ-9 at screening/baseline visit. All subjects will be required to complete a weekly VAS diary for hunger and appetite from screening/baseline until completion of the study. All subjects will be required to complete the TFEQ-R18V2 at enrollment and at each Therapy Visit (Appendix 3). All subjects will be required to complete PHQ-9, TFEQ-R18V2, and Patient Preference Survey at the last study visit (Visit 5 or early termination visit).

#### 9.9 URINE PREGNANCY TESTS (UPT)

A urine pregnancy test will be done in the clinic for all females of child-bearing potential (FOCBP) prior to enrollment in the study. The results will be recorded. This can be completed either at Screening Visit (Visit 0) or Randomization/Enrollment Visit (Visit 1).

#### 9.10 **DIET**

Subjects will be encouraged to maintain a healthy 1200 calorie diet throughout the study. The study doctor and/or research coordinator will provide guidance to assist the subjects on maintaining the diet.

#### 9.11 ELECTRONIC DAILY DIARY DEVICE

For Treatment Group Subjects only, an Android Smart Phone running a semi-custom daily diary application to capture hunger, calories, and weight will be provided. Subjects will be instructed on use by PI or designee.

#### 9.12 STIMULATION

Refer to the Programming Manual provided with the TENS System for full details on the use of the System (Appendix 2). The subject should be instructed to bring their diary (Appendix 5) to the Investigator's office for all office visits to allow for proper downloading of data.

#### 9.12.1 General information on Stimulation:

The TENS unit utilizes low intensity electrical stimulation to activate nerve endings under the skin. While response to TENS varies typically subjects report a mild tingling or burning sensation during and immediately after stimulation session. In addition, mild numbness, termed paresthesia, may be experienced.

#### 9.12.2 Starting the Therapy Phase

During the Therapy Phase, the subject's TENS is programmed to the following settings:

Parameter	Suggested Initial Setting
Frequency	30 Hz
Pulse-Width	200µs
Amplitude	Up to 30 mA sustained (up to 40mA peak)

It is also important that the subject complete the diary during this period. If subject does not feel sensation, subject is to notify PI or Coordinator because it may indicate improper device function. The TENS unit will be replaced if dropped or becomes defective and non-functioning. It is recommended that subjects confirm response to stimulation during the office visits.

#### 10. RISK ANALYSIS

A detailed description of the potential risks associated with specific aspects of the TENS System and diary use are detailed below:

#### 10.1 RISKS

#### 10.1.1 Application and post application risks

While the TENS unit utilized in the present study delivers therapy in a comparable manner to standard commercially available TENS units, there are some risks associated with the device. These include skin irritation at the site of electrode application, numbness and tingling, pain and burning sensations at the site of stimulation. In addition, there is some chance that subjects may feel some gastrointestinal (GI) symptoms including nausea or other GI discomfort (heartburn, dyspepsia, cramping). Dropping the unit may cause damage to the TENS unit. Subjects are instructed to avoid use of the device if it has been damaged in any way and not to use the device while it or any portion of the subject are immersed in water. Subjects are instructed to contact PI or designee, if therapeutic sensation is not present. Any discomfort associated with TENS should be immediately reported to the PI or designee.

#### 10.1.2 Risks associated with appetite loss

While appetite loss is beneficial to weight loss, severe appetite suppression may place the subject at risk for hypoglycemia and dehydration which may entail risks to alertness and other conditions. Prolonged appetite suppression can cause alterations in mood and mental acuity and impact activities of daily living (ADL).

Adverse Events: The adverse events listed below are anticipated to occur at low frequency, and the subject needs to be aware that they may occur.

#### From TENS:

Paresthesia

Burning sensation

Pair

Skin irritation (urticaria) at or near the electrode application site

Redness at site of stimulation

Mild swelling at site of electrode stimulation

Nausea

GI discomfort

Dyspepsia

Heartburn

Cramping

Gastroparesis

From appetite loss:

Mild hypoglycemia

Dehydration

Alterations in mood Mild trouble sleeping Alterations in mental acuity Anorexia

From potential use of anti-nausea medication (PI Discretion):

**Drowsiness** 

**Dizziness** 

Constipation

Stomach upset

Blurred vision

Dry mouth/nose/throat may occur

Mental/mood changes (such as restlessness, confusion)

Difficulty urinating

Fast/irregular heartbeat

From potential use of Cetaphil Moisturizing Lotion

Irritation

Swelling

#### 10.2 MINIMIZATION OF RISKS

Although all of the risks associated with the application and use of the TENS System and their respective frequencies may not be fully known at this time, the preceding risks have been identified through an extensive literature search and represent the most up to date understanding of risks associated with such a study and have been subjected to verification and validation testing to ensure that risks have been mitigated to the extent possible. All efforts will be made throughout the course of the trial to minimize these risks by:

- 1. Selecting an Investigator who is experienced and skilled in weight loss and TENS use:
- 2. Using clearly defined Inclusion/Exclusion criteria to ensure that only appropriate subjects are enrolled;
- 3. Ensuring that the treatment and follow-up procedures are consistent with current medical practices. Each subject will receive more extensive clinical follow-up than would typically be the case for standard care. These additional clinical follow-ups should increase the likelihood of early detection of any adverse events:
- 4. Utilizing a TENS designed so that it can be easily be applied and removed if necessary.

#### 11. ADVERSE EVENTS: DEFINITIONS & REQUIREMENTS

At each evaluation, the Investigator will determine whether any adverse events (AEs) have occurred. For the purpose of this Protocol, an AE is any undesirable clinical occurrence in a subject whether or not related to the investigational treatment. Any pre-existing condition that exhibits a change in nature, severity or degree of incidence during the clinical study is an AE. This definition does not depend on a causal relationship with the device or the Protocol requirements. AEs will be tracked and categorized as outlined within the present protocol.

Subjects are encouraged to report AEs with or without questioning (e.g., How has your health been since the last visit?). If it is determined that an AE has occurred, the Investigator will obtain all the information required to complete the AE Case Report Form.

In addition, subjects will be instructed to contact the Investigator and/or designee if any significant AEs occur between study evaluation visits. Serious AEs and unanticipated adverse device effects will be collected throughout the entire course of the study.

The Investigator will use the following definitions to assess the relationship of the AE to the use of the TENS system and/or daily electronic diary:

Not Related	
 
Not associated with device application
 
Due to an underlying or concurrent illness or effect of another device or drug
 

Unlikely	
 
Little or no temporal relationship to the study device and/or
 
A more likely alternative etiology exists
 

Possible	
 
Temporal sequence between device application and event is such that the relationship is not unlikely or
 
Subject's condition or concomitant therapy could have caused the AE
 

Probable	
 
Temporal sequence is relevant or
 
Event abates upon device application completion/removal or
 
Event cannot be reasonably explained by the subject's condition
 

Highly Probably	
 
Temporal sequence is relevant and
 
Event abates upon device application completion/removal or event recurs on repeated device application
 

#### 11.1 SERIOUS ADVERSE EVENTS

All Serious Adverse Events (SAEs) must be reported to the PI (or designee) and sponsor within 24 hours after any clinical staff member becomes aware of the incident.

An Adverse Event is considered **serious** if the event:

- Led to a death
- Led to a serious deterioration in the health of the subject that:
  - Resulted in a life-threatening illness or injury;
  - Resulted in a permanent impairment of a body structure or a body function;
  - o Required in-subject hospitalization or prolongation of existing hospitalization;
  - Resulted in medical or surgical intervention to prevent permanent impairment to body structure or a body function;

All SAEs need to be followed until the event is resolved (with or without sequelae). The PI or designee will decide if more follow-up information is needed in case the event is not resolved at study completion. In case of death, all possible information that is available (e.g., autopsy or other post-mortem findings), including the possible relationship to the TENS System and/or daily electronic diary should be provided.

#### 11.2 UNANTICIPATED ADVERSE DEVICE EFFECTS

An unanticipated adverse device effect is defined as any adverse effect on health or safety or any life-threatening problem or death caused by, or associated with, a device, if that effect, problem, or death was not previously identified in the Protocol or Supplementary Protocol.

The Investigator must also report the unanticipated adverse device effect to the Institutional Review Board (IRB) within their pre-specified timeline.

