#### 6. STUDY ENDPOINTS

#### 6.1 PRIMARY ENDPOINTS

#### **6.1.1 Primary Safety/ Tolerability Endpoints:**

- Safety/Tolerability will be assessed by the non-inferiority of incidence of serious adverse events (SAEs), unanticipated SAES (USAEs), device-related SAEs (DSAEs) and Unanticipated Device Related SAEs (UDAEs) that are associated with the TENS therapy throughout the therapy/treatment period versus historical control.
- Safety variables will be tabulated and presented for all subjects including enrolled, but discontinued, subjects. Number of subjects undergoing TENS and any reasons for discontinuation of study treatment will be tabulated.

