#### 8.1.1 Safety/Tolerability

The primary safety endpoint is defined as the proportion of subjects free of TENS - related serious adverse events and/or adverse device effects through the therapy phase (safety success rate). The AE and/or ADE rates will be summarized utilizing descriptive statistics and compared utilizing parametric and non-parametric methods as deemed appropriate. The null and alternative hypotheses are:

```
H_0: π_T ≤ π_C
H_1: π_T > π_{C}
```

Where  $\pi_T$  and  $\pi_C$  are the probabilities of adverse events and/or adverse device effects in treatment versus historical control respectively.

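### Section 11.2 tests only whether a device effect has been named, so a serious form of an ungraded listed effect can be classed as anticipated and left out of the unanticipated counts and reports

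*Combined protocol and SAP*

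**What the plan says.** Section 11.2 covers "any adverse effect on health or safety or any life-threatening problem or death caused by, or associated with, a device", and calls it unanticipated "if that effect, problem, or death was not previously identified in the Protocol or Supplementary Protocol". The investigator must report such an effect to the IRB on the IRB's own timeline. Section 12.5 names unanticipated adverse device effects among the sponsor's reports to regulators and sites; it does not name SAEs.

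The effects identified in advance are listed at the end of section 10.1.2, under stimulation and under appetite loss. They are introduced as "anticipated to occur at low frequency", with no rate. A few entries carry a grade, for example "Mild hypoglycemia". Most carry none.

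The primary safety endpoint in section 6.1.1 is a non-inferiority comparison of four classes of event. Three are SAEs overall, those related to the device, and those that are unanticipated (USAEs). The fourth is given as "Unanticipated Device Related SAEs (UDAEs) that are associated with the TENS therapy throughout the therapy/treatment period versus historical control". Neither unanticipated class (USAE, UDAE) is defined there or elsewhere. Section 8.1.1 defines the analysed endpoint as the "proportion of subjects free of TENS - related serious adverse events and/or adverse device effects through the therapy phase" and makes no use of whether an event was anticipated.

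**The concern.** Whether an effect is expected normally depends on what was foreseen about it, including how bad and how common it would be. Here the label alone decides. Once a term is on the list, a case that puts the subject in hospital can be treated in the same way as a passing symptom of the same name.

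Two things depend on that classification. The first is reporting: unanticipated device effects have their own IRB report in 11.2 and are the only adverse-event category that 12.5 names for the sponsor's reports. The second is the primary safety endpoint, where two of the four classes are unanticipated events. If 11.2 is the rule applied to them, the unanticipated device class could read zero while serious device harm occurs under a listed name.

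**Working it through.** The plan gives no rate, margin or historical figure for unanticipated events, so it has no figure of its own to reproduce. The check compares sections and adds one illustration of scale.

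**1. Count of listed terms (section 10.1.2).** Stimulation: 12. Appetite loss: 6. Total 12 + 6 = 18. Three are entered as mild (swelling, hypoglycemia, trouble sleeping), which leaves 18 − 3 = 15 ungraded. The separate lists for anti-nausea medication and lotion are not counted.

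**2. Grades elsewhere in the protocol.** Section 9.12.1 describes burning sensation and paresthesia as mild. Because 11.2 refers to the Protocol as a whole, those two may be taken as graded, leaving 15 − 2 = 13. Gastroparesis, dehydration, nausea and anorexia are among the 13. In the other direction, the text of 10.1.2 also names hypoglycemia as a risk of severe appetite suppression without calling it mild, so that grade is not firm.

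**3. Following one event through the text.** Take a subject admitted to hospital with gastroparesis judged related to the device.

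| Section | Result |
|---|---|
| 11.1 | Serious, because of the admission; goes to the PI and sponsor within 24 hours |
| 11.2 | Gastroparesis is named in the Protocol, so the event can be read as anticipated; no report under 11.2 |
| 12.5 | Not in the named category of unanticipated device effects |
| 6.1.1 | Counts as an SAE and as a device-related SAE; not as a UDAE if 11.2 is the test |
| 8.1.1 | Counts as a failure |
| 13.1, 16.1 | IRB still informed of it as an SAE |

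**4. Match between 11.2 and 6.1.1.** Section 11.2 has no seriousness limit; the UDAE class in 6.1.1 contains only serious events. No section says that one defines the other. Section 11.2 concerns device effects only, so the USAE class has no stated test at all.

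**5. Wording the protocol already uses.** The general AE definition in section 11 takes changes in nature, severity and incidence into account for pre-existing conditions. Section 11.2 does not carry that idea over.

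**6. Illustration of scale (assumed rates; the documents give none).** If a serious form of an ungraded listed effect has true risk p, the chance of at least one case in n treated subjects is 1 − (1 − p)^n. The planned n is 75 (section 8.2). The value 150 assumes that the maximum of 300 is enrolled and split equally.

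| p | Expected cases, n = 75 | Chance of ≥1, n = 75 | Chance of ≥1, n = 150 |
|---|---|---|---|
| 0.5% | 0.375 | 31% | 53% |
| 1% | 0.75 | 53% | 78% |
| 2% | 1.5 | 78% | 95% |
| 5% | 3.75 | 98% | over 99.9% |

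For example, 1 − 0.99^75 = 0.53. On a name-only reading, each such case adds 0 to the UDAE count, unless it is itself a death or life-threatening problem.

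**The case against.** The strongest reply is that little depends on this classification. Section 16.1 obliges the site PI to keep the IRB informed of SAEs and serious device effects whether or not they were expected, section 13.1 adds SAE reports at the IRB's request, and section 11.1 sends every SAE to the PI and sponsor within 24 hours. The unanticipated classes sit inside the SAE and device-related SAE classes, which still count the event, and 8.1.1 does not use expectedness. This stands, and it limits the consequence to the label, the reporting route and timeline, and the unanticipated counts.

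A reader might infer that a listed effect can never be unanticipated. The text does not support that. Deaths and life-threatening problems are separate limbs of 11.2 and are not on the list. A severe form of a term entered as mild can be read as not identified. A burn injury is arguably not the listed burning sensation. The stated low frequency also gives some basis, though unquantified, for treating an unexpectedly common effect as unanticipated.

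A reader might also infer that frequent listed symptoms are missing from the UDAE count. Non-serious events could not enter it under any definition, because 6.1.1 restricts that class to serious events. For those events the frequency gap matters for reporting only.

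Finally, the link from 11.2 to the endpoint class is an inference. That is correct, but it leaves two primary-endpoint classes without a definition, and 11.2 is the nearest text an analyst would turn to.

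**Conclusion.** The point holds in a limited form. Followed as written, 11.2 allows a serious, non-life-threatening case of an ungraded listed effect to be classed as anticipated. This affects 15 of the 18 listed terms, or 13 if the descriptions in 9.12.1 count as grades. Such a case can be left out of the reports in 11.2 and 12.5 and, on the assumption that 11.2 is the test for UDAE, out of that component of the primary safety endpoint.

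It would be wrong to conclude that the primary safety result as a whole is understated. Provided the event is judged device-related, which the UDAE class requires as well, it still counts as an SAE, a device-related SAE and a failure in 8.1.1. No figure in the plan changes. The matter is still worth correcting, because it concerns a stated rule that can misclassify serious events, and at assumed risks of 1% to 2% at least one such event among 75 treated subjects is more likely than not (53% to 78%).

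**What to change.** - **Section 11.2:** reword so that an effect is unanticipated when its nature, severity or frequency goes beyond what the protocol has identified.
- **Section 10.1:** state that the listed effects are expected as non-serious, and give the frequency expected for each, so that there is a reference to judge against.
- **Section 6.1.1 and the matching Protocol Summary text:** define USAE and UDAE as the serious subset of the section 11 terms. Tabulate non-serious, unlisted device effects separately.

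The cost is protocol and case report form wording, and possibly a few more IRB and regulatory reports. Sample size and the analysis in 8.1.1 are unaffected.

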### 12. SPONSOR RESPONSIBILITIES, RECORDS, AND REPORTS

#### 12.1 GENERAL RESPONSIBILITIES

The Principal Investigator (PI) maintains the overall responsibility for this study including ensuring that the study is conducted according to the regulatory requirements of the United States Food and Drug Administration (FDA) (Code of Federal Regulations Title 21), Good Clinical Practice (GCP), the Declaration of Helsinki, and other applicable regulatory requirements, the Protocol, and any conditions of approval imposed by the Institutional Review Board (IRB) and the relevant Competent Authorities. The PI will adhere to general duties as outlined by 21 CFR and GCP.

#### 12.2 SELECTION OF CLINICAL INVESTIGATORS SITE

The PI and the site are qualified according to these criteria:

- Adequate subject population available to meet the requirements of the study
- Adequate time to be personally involved in the study
- Adequate research staff and resources to support the study
- Willingness to take the primary responsibility for the accuracy, legibility, and security of all study data
- Willingness to observe confidentiality at all times
- Associated with an IRB which satisfies all regulatory authority requirements and conducts meetings on a regular basis
- Access to appropriate emergency medical facilities if needed
- Other requirements as previously noted in Protocol

#### 12.3 TRAINING OF INVESTIGATOR AND SITE PERSONNEL

The training of the Investigator and appropriate clinical site personnel will be the responsibility of the PI, or designee, and may be conducted during a site initiation visit or other appropriate meetings.

#### 12.4 MONITORING

A Monitor will be assigned to perform source document review to be performed against entries on the Case Report Form for 100% of the data related to safety and performance outcomes, and a quality assurance check will be performed to ensure that the Investigator is complying with the protocol and regulations.

All data entered by the subject onto the electronic diary will be uploaded onto a secure, central database. The data in the database are considered source documentation and are protected by auditable change logs. The data and change logs may be monitored by the Clinical Data Monitor to confirm data integrity. Further efforts to ensure data privacy and integrity include the removal of the network interface (a.k.a. SIM) card from the handheld Smart Phones used in the study to ensure that only controlled data download/upload conducted by study coordinators can occur.

At the completion of the study, the assigned monitor will perform a close-out visit to ensure that all clinical trial materials and subject data are properly documented.

If a member of the research team becomes aware that any individual associated with the study is not complying with the signed Investigator Agreement, the Protocol, the Declaration of Helsinki, or other applicable regulatory requirements, or any conditions of approval imposed by the IRB or Regulatory Authorities, the PI will either secure compliance or, failing to secure compliance, will discontinue the individual's participation in the investigation.

#### 12.5 REPORTS

The sponsor will submit appropriate reports to the Regulatory Authorities or the investigational site as identified by local regulations. These include unanticipated adverse device effects, withdrawal of IRB approval or Regulatory Authority approval, annual progress reports, recall information, final reports and device use without Informed Consent.

#### 12.6 RECORD MAINTENANCE

The clinical site will maintain study records for at least seven (7) years after the study is terminated or according to site and country specific requirements.

#### 12.7 REGULATORY AUDITS

The Investigator and/or designee must be available to respond to reasonable requests and audit queries made by authorized regulatory representatives during the audit process.

